9.4 Statistical Analyses

9.4.1 General Approach

Descriptive statistics:

- The number of subjects who utilized the protective device will be included; the level of experience and training of user subjects will be included.
- Patient subject baseline demographics, co-morbidities, smoking status, and intubation-related factors will be included.
- Objective data regarding total time for the airway procedure, number of intubation/LMA/extubation attempts, airway device used (i.e. intubation blade used and size of ETT) will be included.
- The user subjects comfort level for device use will be graded on a continuous scale, and the mean comfort level calculated as well as the range.
- The patient subjects comfort level and experience in the device will be graded on a continuous scale, and the mean comfort/experience level calculated as well as the range.
- Categories for various healthcare burdens will be provided as options for participants; the mean for most common burden will be identified; the percentage for each burden subtype will also be identified.

Inferential Tests

- A p-value of 0.05 and 95% confidence interval will be utilized when determining if the protective device results in an improvement in outcomes measures, i.e. a decrease in the number of COVID-19 cases by participants.
- Chi-square testing or ANOVA will be used.

Covariates will be collected on participants, including but not limited to subspecialty training, years of experience as a resident, fellow, or attending, as well as gender.

Assumption of normality of data points will be determined using Q-Q plots. If there are limitations to performing assumptions of normality, then appropriate non-parametric corrections would be performed.

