5.2 Exclusion Criteria

An individual who meets any of the following criteria will be excluded from participation in this study.

A) User Subjects (healthcare workers):

1. Pregnancy (due to potential risks from lifting the device)

B) Patient Subjects:

1. Known history of difficult airway
2. Anticipated difficult airway management for any reason
3. COVID-19 positive status
4. Planned prolonged intubation post-surgery or anticipated inability to answer patient questionnaire within 1 week of intubation.

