Patient Subject Experience Survey: The patient subject's randomized to device use will be asked in the recovery room post-procedure or receive a phone call or email with REDCap survey link from a qualified study coordinator to answer a short patient experience survey where the data will be collected in REDCap and subsequently transcribed into CTMS. Data collected will include: 1) overall comfort in the device, 2) sensation of increased anxiety, 3) sensation of claustrophobia, 4) perceived safety in the device, 5) any difficulties seeing or hearing while in the device, 6) any additional comments or suggestions regarding the experience in the device. All data will be collected on a Likert scale and stored in CTMS.

Patient subjects' medical records medical will be accessed as part of the study. Personal and medical data collected as part of the study will be stored in a de-identified fashion on an institutionally secured and managed network drive and/or computer.

As part of this study, user subjects' medical records will NOT be accessed. Personal data including age, and gender, will be collected as part of the initial data collection instrument and stored in de-identified fashion on an institutionally secured and managed network drive and/or computer.

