9 STATISTICAL CONSIDERATIONS

9.1 *Statistical Hypotheses*

We hypothesize that the biocontainment device will be a safe and effective option for performing airway procedures in patients while also providing additional protection during an aerosol generating procedure.

Primary Efficacy Endpoints:

1. We hypothesize that the time to perform an airway procedure with the biocontainment device will be equivalent to time for airway procedure without the biocontainment device. Alternatively, there will be prolonged airway procedures times with the device. This endpoint will be analyzed every two weeks.
2. We anticipate that the number of AEs or ADEs will be low and will also decrease over time. This endpoint will be analyzed on a weekly basis.

Secondary Efficacy Endpoints:

1. We hypothesize that the median Likert ratings for User subject device comfort will be weighted toward “strongly agree”. Alternatively, we will see ratings favoring “neutral” or “disagree” for user subject device comfort.
2. We hypothesize that the median Likert ratings for User subject additional healthcare burden comfort will be weighted toward “strongly disagree”. Alternatively, we will see ratings favoring “neutral” or “agree” on increased healthcare burden.
3. The median Likert ratings for the Patient Experience survey will be weighted toward minimal patient discomfort or anxiety. Alternatively, we will see ratings favoring increased patient discomfort or anxiety inside the device.
3. We anticipate that the median Likert ratings of the patient experience post-survey will indicate overall good user comfort and low levels of anxiety or claustrophobia in the device.

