9.2 Sample Size Determination

Statistical calculations:

Sample size (for unknown population size) was determined based upon a 95% confidence level (Z-score 1.96), standard deviation of 0.5, and a margin of error (confidence interval) of 10%. [[qualtrics.com/experience-management/research/determine-sample-size](https://www.qualtrics.com/experience-management/research/determine-sample-size)]

- Necessary Sample Size = $((Z\text{-score})^2 * \text{StdDev}^2 * (1-\text{StdDev}^2)) / (\text{margin of error})^2$
 - $((1.96)^2 * 0.5^2 * (1-0.5^2)) / (0.1)^2 =$
 - $(3.8416 * 0.25) / (0.01) =$
 - 96.04
 - **At least 97 performed airway procedures are needed to have adequate power to test our hypotheses for this study**

We will screen at least 175 patients, and assuming a 10-15% drop-out/screen failure rate, plan to enroll at least 150 patient subjects on a rolling basis during weeks 2 - 6 of the trial to evaluate the use of a novel biocontainment and aerosol evacuation system. The study should be adequately powered to assess secondary endpoints. Some of the sub-analyses may be underpowered depending on the characteristics of the recruited patients.

At defined intervals (see Section 1.3 Schema), we will perform interim analysis to determine changes to sample size based on subject drop out/withdrawal.

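### Section 9.4.1 ties the 0.05 level to fewer COVID-19 cases, which is not a trial endpoint, and no margin or rule tests the stated equivalence of airway procedure time

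*Combined protocol and SAP*

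**What the plan says.** Under the inferential tests in section 9.4.1, the plan states: "A p-value of 0.05 and 95% confidence interval will be utilized when determining if the protective device results in an improvement in outcomes measures". The sentence goes on to specify the improvement as "a decrease in the number of COVID-19 cases by participants". The next bullet adds only that chi-square or ANOVA will be used.

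The primary time hypothesis in section 9.1 is that "the time to perform an airway procedure with the biocontainment device will be equivalent to time for airway procedure without the biocontainment device". Its alternative is: "Alternatively, there will be prolonged airway procedures times with the device". The primary safety hypothesis reads: "We anticipate that the number of AEs or ADEs will be low and will also decrease over time".

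Section 9.4.2 defines procedure time from T0 (mask removal) to T1 (airway device connected to the circuit). It assigns ANOVA to the comparison with and without the device, adds a multiple regression, and uses logistic regression for AEs and ADEs. Section 9.4.3 assigns chi-square tests to the three Likert endpoints. Neither section gives a significance level, a margin or a rule for declaring equivalence.

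**The concern.** The sentence in 9.4.1 is the only one in section 9 that attaches the 0.05 level to a named outcome, and that outcome is not one the trial sets out to measure. Its direction is also wrong for the main question: it looks for improvement, whereas 9.1 asks whether procedure time is equivalent or prolonged.

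Two things are at stake. First, the clause leaves room for a claim of protection against infection that the data could not support. Second, once the clause is set aside, what remains for procedure time is a test of difference with no margin, so failure to reach significance could be reported as the hypothesized equivalence. This could matter before the final analysis. Section 9.1 has the time endpoint analysed every two weeks, 9.4.5 plans an interim analysis of primary and secondary outcomes, and 10.1.2 lists efficacy, the primary endpoint being met, and futility among possible grounds for stopping. For the time hypothesis, none of these can be judged without a limit.

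**Working it through.** **1. Is COVID-19 infection a trial outcome?**
- Objectives and endpoints (1.1, section 3): procedure time, AEs/ADEs, user comfort and burden, patient experience, design feedback. No infection outcome.
- Hypotheses (9.1): none on infection.
- Data items (8.1): the safety items are injury, perceived anxiety or claustrophobia, difficulty intubating, and device defects. No COVID-19 test or infection follow-up is listed.
- Expected events (8.3.2.3) and Schedule of Activities (12.1): no infection item.
- Section 8.1 says that user subjects' "medical records will NOT be accessed".
- Patients with "COVID-19 positive status" are excluded (5.2), so the study procedures are not designed to expose users to the hazard in either arm.
- Incidental route: intercurrent illnesses count as AEs (8.3.1.1), and AEs are reported from consent to study completion (8.3.4). A case could therefore be recorded, but without systematic ascertainment.

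**2. Could a case be assigned to an arm?** Patients are randomized 2:1 (6.3), 100 with the device and 50 without (1.3), from the case-loads of participating anesthesiologists (5.5). The 15 to 20 users are not randomized and may work in both arms, so a user's infection belongs to neither. A patient's infection would have an arm, but no infection follow-up is planned.

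**3. Does the sample size supply a rule for time?** Section 9.2 uses "95% confidence level (Z-score 1.96), standard deviation of 0.5, and a margin of error (confidence interval) of 10" per cent.
- n = z² p(1 − p) / e² = 1.96² × 0.25 / 0.10² = 96.04, rounded up to 97. This reproduces the stated figure.
- The formula as printed gives 3.8416 × 0.25 × 0.75 / 0.01 = 72.03, rounded up to 73. The plan's next line drops the factor 0.75.
- The 97 is therefore a one-sample precision figure: a half-width of 10 percentage points for a proportion of 0.5. It contains no time difference, SD of time, margin, power or infection rate.

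**4. What would a non-significant result on time mean?** The documents give no SD of procedure time, so the following is in SD units. It assumes independent observations, equal SDs and a normal approximation.
- SE = √(1/50 + 1/100) = 0.1732 SD.
- Power of a two-sided 0.05 test ≈ Φ(d/SE − 1.96), where d is the true difference:

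| True prolongation d | Power | Chance of a non-significant result |
|---|---|---|
| 0.3 SD | 41% | 59% |
| 0.4 SD | 64% | 36% |
| 0.5 SD | 82% | 18% |

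**5. What limit could 100 versus 50 support at 80% power if the true difference is zero?**
- One-sided (upper end of the 95% CI below the limit): (1.960 + 0.842) × 0.1732 = 0.49 SD.
- Two-sided (95% CI inside ± the limit): (1.960 + 1.282) × 0.1732 = 0.56 SD.
- Two one-sided tests at 0.05 (equivalently, a 90% CI inside ± the limit): (1.645 + 1.282) × 0.1732 = 0.51 SD. With this rule, power is about 7% for a margin of 0.3 SD, 49% for 0.4, 79% for 0.5 and 93% for 0.6.

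The limit and the side of the claim therefore decide what the trial can conclude, and neither is stated.

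**The case against.** The strongest reply is that the COVID-19 clause is a misplaced example. Section 8.1 uses the same abbreviation loosely to introduce examples of co-morbid conditions and device defects, and the main clause in 9.4.1 is general. The section that governs primary inference is 9.4.2, which can be carried out without the clause, and the study is described as one of safety and feasibility. On this view the correction is one of wording.

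Much of this stands, and it rules out several stronger readings that a reader might infer:
- *That 9.4.1 holds the plan's only inferential criterion.* It does not: 9.4.2 names ANOVA and regression models, and 9.4.3 names chi-square tests.
- *That no COVID-19 data can exist.* This is too absolute. A case could be recorded incidentally as an AE, and patient records are accessed. The supportable statement is that nothing is systematically ascertained.
- *That no infection could be attributed to an arm.* This holds for users only, since patients are individually randomized.
- *That the clause is the trial's success criterion.* The documents never call it that.

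The reply does not rescue the plan's inference. Even as an example, the clause names an outcome outside the endpoints and a direction that 9.1 does not hypothesize. Relying on 9.4.2 then exposes the second gap: ANOVA tests for a difference, and a non-significant result does not establish equivalence. It is fair to say that this gap would remain if the clause were simply deleted, so the correction must reach 9.4.2 as well.

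**Conclusion.** The concern holds in this form. Section 9.4.1 links the 0.05 level to an outcome that is not an endpoint, would be captured at most incidentally, and for users cannot be tied to an arm. Section 9.4.2 does provide a test of procedure time, but not one that addresses equivalent versus prolonged time, and no margin appears anywhere in the documents.

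The absence of infection as a planned outcome and the absence of a margin follow from the text alone. The size of the risk of misreading depends on the assumptions stated above: a true prolongation of 0.3 to 0.4 SD would go undetected in roughly 59% to 36% of such trials. How many seconds that represents, and whether it matters, cannot be said from the documents. The point should be corrected before analysis. It does not prevent the planned data from being collected or the time comparison from being made.

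**What to change.** 1. In 9.4.1, delete the COVID-19 clause and state that no inference on infection risk will be made.
2. In both 9.4.1 and 9.4.2, state that the device-minus-control difference in airway procedure time (T1 − T0) will be estimated with a 95% CI and judged against a pre-stated, justified limit, and that a non-significant ANOVA will not be read as equivalence.
3. Align 9.1 with this by saying whether the claim is equivalence (two-sided) or no unacceptable prolongation (one-sided). If equivalence is to be shown by two one-sided tests at 0.05, say so, because that corresponds to a 90% interval.
4. Do not cite the 97 procedures in 9.2 as power for this comparison. Instead, give the precision or power of 100 versus 50 for the chosen limit, with an assumed SD.

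No new data collection is needed. The cost is more than an edit to one sentence: the sponsor must choose and justify the limit before the time results are seen, and may find that the planned numbers support only a wide one. The trial gives up a claim about infection that it could not have supported.

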9.4.2 Analysis of the Primary Efficacy Endpoint(s)

Primary Endpoints:

1. Assessment of time to complete an airway procedure with or without the biocontainment device. The time is measured as a single quantitative measure at the end of the procedure. The initial starting time (T0) is defined as “time the mask is removed from the patient just prior to initiation of the airway procedure”. End time (T1) is defined as the time that the airway procedure is completed with a secure airway defined as the

time the airway device is secured to the airway circuit. Data will be presented as median amount of time for a given procedure with or without the biocontainment device and statistical significance will be determined by analysis of variance (ANOVA). Additionally, a multiple regression model will be created using covariates of subject user experience, number of prior uses with the device, and patient specific factors (co-morbid conditions, BMI, Mallampati score). This will help determine the critical factors associated with time to use the device.

2. The total number of AEs and ADEs will be presented. This will be broken down by specific AE or ADE. Logistic regression will be used to assess possible contributing factors to AEs or ADEs including subject user experience, airway procedure performed, patient-specific factors (BMI, co-morbid conditions, Mallampati score). We anticipate a low number of AEs/ADEs and as such, statistically rigorous regression analyses may be limited by a low overall number of events.

Statistical analyses will be performed on all data points, however, a sub-analysis will be performed on participants without any missing data points.

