1 STUDY SUMMARY

1.1 Synopsis

Title: Aerosol Biocontainment Device (ABCD) with Aerosol Clearance for Aerosol Generating Procedures

Short Title: Aerosol BioContainment Device (ABCD)

Study Description: The primary goal of this study is to assess use of a biocontainment device for planned airway procedures under general anesthesia. This will serve as a platform for using this device as a novel biocontainment and aerosol evacuation system as part of rapid sequence intubation protocols for COVID-19 patients. We hypothesize that airway procedures with the aerosol biocontainment device will be safe and effective with airway procedure times approaching times for airway procedures without the device.

Objectives: The primary objectives of this study are: 1) Assess changes in airway procedure time with and without the biocontainment device as a function of repeated utilization and as a function of patient-associated airway factors (i.e. Mallampati score, hyomental distance, neck mobility, BMI) and user-associated airway factors (i.e. experience of user, airway device used, induction sequence) 2) Assess adverse events, adverse device events associated with biocontainment device use.

Secondary objectives include: 1) Assess the subject's comfort with using the biocontainment device. 2) Assess for additional healthcare and cognitive burden imposed by the device. 3) Survey of patient's post-procedure on experience being inside the device. Exploratory objectives include gathering specific feedback regarding possible design modifications for further iterations and design improvements with the engineering team.

Primary Endpoint: The primary endpoints of this study are:
1. Measuring the time for performing an airway procedure with the biocontainment device when accounting for patient and user-specific factors.
2. Quantifying the number of AEs or ADEs over time to assess device safety.

Secondary Endpoints: The secondary endpoints include:
1. Median Likert ratings from device use survey questions that assess user subject device comfort.
2. Median Likert ratings from device use survey questions that assess user subject healthcare burden with the device.
3. Median Likert rating of the patient questionnaire results to assess patient experience in the device.

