4 STUDY PLAN

4.1 Study Design

This is a multi-site (HUP, PPMC), unblinded, randomized, observational study performed in a controlled environment in the operating room. The hypothesis is that rapid sequence intubation or other urgent airway procedures performed with the biocontainment device will be safe and can be performed in an equivalent manner to urgent airway procedures without the biocontainment device. Methods to minimize bias include randomizing patients to intubation with or without the biocontainment device. Stratification of results will be performed as described in [Section 9.4.7](#) below.

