9.4.5 Planned Interim Analyses

An interim analysis will be performed after 50% enrollment (approximately 4 weeks) on primary and secondary outcomes. If the total number of AEs or ADEs is trending upward over time, the study would be paused until further assessment of AE/ADEs by the study Sponsor or their qualified designee would be performed as described in [Section 8](#).

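### The primary hypothesis is equivalent airway time, but the plan tests for a difference and sets no margin on time, so a non-significant result could be read as equivalence without showing it

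*Combined protocol and SAP*

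**What the plan says.** Section 9.1 gives the first primary hypothesis: "the time to perform an airway procedure with the biocontainment device will be equivalent to time for airway procedure without the biocontainment device". The alternative follows at once: "Alternatively, there will be prolonged airway procedures times with the device". The synopsis (1.1) words the aim more loosely, as "airway procedure times approaching times for airway procedures without the device". Section 4.1 hypothesises that urgent procedures with the device "can be performed in an equivalent manner to urgent airway procedures without the biocontainment device".

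Section 9.4.2 presents median times by arm and then says "statistical significance will be determined by analysis of variance (ANOVA". It adds a multiple regression on user experience, prior device uses and patient factors.

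Section 9.4.1 names p = 0.05 and a 95% confidence interval, but for use "when determining if the protective device results in an improvement in outcomes measures", with COVID-19 cases among participants as the example. Section 9.2 derives a minimum of 97 procedures and says this gives "adequate power to test our hypotheses for this study".

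On timing, 9.1 has the time endpoint analysed every two weeks, and 9.4.5 adds: "An interim analysis will be performed after 50% enrollment (approximately 4 weeks) on primary and secondary outcomes".

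**The concern.** An ANOVA takes equal means as its null hypothesis and can only produce evidence against it. Section 9.1 makes equivalence the position that stands unless prolongation is shown, which is the reverse of an equivalence set-up. It invites the reading that p > 0.05 confirms the hypothesis.

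To support equivalence, the data must exclude every difference that the investigators would regard as too large. That requires a stated margin, and the plan has none. Airway time is the first primary endpoint. A report could call the times equivalent when the data are still compatible with a prolongation that the investigators would not accept, and nobody could say beforehand which results would rule that out.

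**Working it through.** **1. Is there a margin or rule elsewhere?** The only margin in the plan is the 10% margin of error in 9.2. Its worked line is 1.96² × 0.25 / 0.10² = 3.8416 × 0.25 / 0.01 = 96.04, rounded up to 97, so the stated figure reproduces. (The formula as printed, with SD²(1 − SD²), would give 3.8416 × 0.25 × 0.75 / 0.01 = 72.03.) This is the precision of a single proportion near 0.5. It contains no time difference, no SD of time and no comparison of arms.

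The 95% interval in 9.4.1 is tied to improvement and set against no bound. The regression in 9.4.2 looks for factors associated with time, and the non-parametric fallback in 9.4.1 is unspecified. Neither supplies a decision rule.

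**2. How often would a real prolongation be non-significant?** Inputs: 100 with the device and 50 without (1.3), allocated 2:1 (6.3), two-sided 0.05. Assumed: effects in SD units, equal SDs, independent procedures. The standard error is SD × √(1/n₁ + 1/n₂), and the probabilities come from the noncentral t distribution.

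| True prolongation | 100 vs 50 (SE 0.173 SD) | 50 vs 25, the 50% look (SE 0.245 SD) |
|---|---|---|
| 0.25 SD | 70% | 83% |
| 0.35 SD | 48% | 71% |
| 0.50 SD | 18% | 48% |

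**3. What would a non-significant result leave open?** At 100 vs 50 the 95% half-width is t(0.975, 148) × 0.1732 = 1.976 × 0.1732 = 0.342 SD. An estimate just short of significance is itself about 0.342 SD, so its upper limit is about 2 × 0.342 = 0.68 SD.

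**4. What could an interval rule deliver at this size?** Take no true difference and margin m. Approximate power is Φ(m/SE − 1.976) when the upper 97.5% limit must lie below m. It is 2Φ(m/SE − 1.655) − 1 when a 90% interval must lie within ±m (two one-sided tests), and 2Φ(m/SE − 1.976) − 1 for a 95% interval. At m = 0.5 SD, m/SE = 2.887. The figures below are from simulation with the SD estimated, and they agree closely with these formulas.

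| Margin | Upper 97.5% limit | 90% interval | 95% interval |
|---|---|---|---|
| 0.5 SD | 82% | 78% | 64% |
| 0.4 SD | 63% | 49% | 26% |
| 0.3 SD | 40% | 7% | <1% |

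The margins giving 80% power are about 0.49, 0.51 and 0.565 SD. By normal approximation, the total size at 2:1 for 80% power with the 90% interval rule is 156 at 0.5 SD, 243 at 0.4 SD and 429 at 0.3 SD.

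**5. Repeated looks (a lesser point).** If each look were a formal test at |Z| > 1.96, the false-positive rate for a difference would be 8.3% with looks at 50% and 100% of the data. It would be 10.7% with looks at thirds and about 11% with looks at 25%, 50% and 100%. More two-weekly looks would raise it further.

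**The case against.** The strongest reply is that equivalence appears in the hypotheses but not in the formal objective or endpoint. Sections 1.1 and 3 speak of assessing changes in time with repeated use and with patient and user factors, and 2.2 and 4.2 describe a safety and feasibility study. The regression in 9.4.2 serves that objective. No section says that p > 0.05 will be taken as equivalence, and the wording in 4.1 does not mention time.

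All of this is accurate. It shows that the plan could be repaired by dropping the equivalence claim. It does not reconcile 9.1 with 9.4.2 as they stand: the trial is randomised, states an equivalence hypothesis for a primary endpoint and claims power for its hypotheses.

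Three further points stand as limits:
- The power figures favour the plan. They take all 150 procedures as analysed, although 9.3 specifies a per-protocol dataset. They pool procedure types, although 9.4.2 reports time for a given procedure. They ignore variation in the device effect among about 15 users.
- The fix is cheap only if the margin is about 0.5 SD or wider. A tighter margin needs more procedures or a more modest conclusion.
- The repeated-look rates assume formal tests that the plan does not specify. The action that 9.4.5 attaches to its interim analysis concerns adverse-event trends, and 9.2 ties interim analysis to sample size after drop-out.

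**Conclusion.** The concern holds, and it should be settled before any time data are compared by arm. The hypothesis in 9.1 and the test in 9.4.2 do not match, and nothing else in the plan states which time result would support equivalence. This is an error in the plan as written rather than missing detail, because following it exactly could not establish its first primary hypothesis.

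With the planned arms, a true prolongation of 0.35 SD would go undetected about half the time. These figures cannot be turned into seconds, because the documents give no SD of time.

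The interim point is secondary. Section 10.1.2 lists efficacy, futility and the primary endpoint having been met among possible stopping reasons, but no p-value is tied to any of them. The status of interim time results is therefore undefined.

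**What to change.** In 9.1 and 9.4.2, replace the ANOVA p-value as the decision rule with the estimated device-versus-control difference or ratio in airway time and its confidence interval. Choose the scale in advance, since 9.4.2 currently reports medians but tests with ANOVA, which compares means. Then take one of two routes:

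- **Keep a claim.** The investigators fix a margin and state which rule applies: equivalent if the whole interval lies inside the margin, or not meaningfully prolonged if its upper limit lies below it. Rework 9.2 for that margin using an SD of time.
- **Drop the claim.** Reword 9.1, 1.1 and 4.1 as estimation, and report the estimate and interval with no statement of equivalence. This suits the feasibility aim and needs no added patients.

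Two small related edits:
- State in 9.1 and 9.4.5 that interim time summaries are descriptive and only the final analysis carries inference, or adopt a group-sequential boundary.
- Delete the COVID-19-cases example from 9.4.1, since the data collection in 8.1 does not include that outcome.

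The cost is protocol wording and agreement on one margin and one rule, with no new data items. The downside is a possibly more modest conclusion or, if the margin is well below 0.5 SD, a larger trial.
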